12.0 SELECTION OF SUBJECTS

12.1 Study Population

This study will enroll approximately 40 subjects diagnosed with COVID-19 who are at risk for developing acute respiratory distress syndrome (ARDS) receiving standard of care including anticoagulation. Randomization of subjects will be stratified by use of IL-6 antibody therapy.

Subjects who do not meet all of the inclusion criteria or who meet any of the exclusion criteria are not eligible to participate in the study.

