13.8 Prohibited Medication

The use of any unauthorized investigational therapy is prohibited during the study.

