15.2 Randomization

Once all of the screening assessments have been conducted, subject will be randomized. Randomization will be stratified according to subject's use of IL-6 antibody therapy and may occur on either the last day of screening or the morning of Day 1.

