10.1 Primary Efficacy Variable Analysis

The co-primary efficacy endpoints are listed below. The primary analysis for each of these two endpoints will be conducted using Pearson's chi-square tests. Because study success is defined as success on both, each of the two co-primary endpoints will be tested using a one-sided significance level of 0.025.

- Proportion of subjects free from respiratory failure
 - Calculate the proportion of the subjects free from supplemental oxygen (invasive mechanical ventilation, non-invasive ventilation, high-flow oxygen, ECMO, CPAP, BiPAP, nasal cannula) at Day 7
- Proportion of subjects with improvement in clinical status using the NIAID 8-point ordinal scale and discharge record at Day 7
 - Calculate the proportion of the subjects who improved at least one-point from baseline

For each of the two co-primary endpoints, subjects whose response status is unknown will be assumed to be nonresponders.

A supportive analysis for each of the two co-primary endpoints will be conducted using the Mantel-Haenszel test stratified by the randomization stratification variable (use of IL-6 antibody therapy).

Confidential

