10.2 Secondary Efficacy Variable Analysis

The secondary efficacy endpoints are the following:

- Proportion of subjects free from respiratory failure as defined by free from supplemental oxygen requirement (invasive mechanical ventilation, non-invasive ventilation, high-flow oxygen, or ECMO, CPAP, BiPAP, nasal cannula) at Days 14, 28 and Day 60* Proportion of subjects with mechanical ventilation /intubation at Days 7, 14, 28 and Day 60*
- Change from baseline in clinical status using NIAID 8-point scale and discharge record at Days 7, 14, 28 and 60* Proportion of subjects with at least a one-point improvement in clinical status using the NIAID 8-point ordinal scale and discharge record at Day 14, 28 and 60*
- All-cause mortality at Days 28 and Day 60* Proportion of the subjects discharged from hospital at Day 7, 14, 28 and 60*
- Change from baseline in migration inhibitory factor (MIF), (interleukin 1-beta (IL-1 β), interleukin 6 (IL-6), tumor necrosis factor (TNF- α), and C-reactive protein (CRP) at Day 3, 5, 7 and 14

*Intubated subjects only on Study Day 60

All secondary endpoints that are defined as proportion variables will be analyzed using Pearson's chi-square tests. Secondary endpoints that are defined as the change from baseline will be analyzed using analysis of covariance (ANCOVA) models with treatment group as a factor and the baseline value of the corresponding endpoint as a covariate. All secondary analyses will be conducted using one-sided tests at the alpha=0.025 level of significance, with no adjustments for multiplicity.

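### The SAP 10.2 ANCOVA omits the randomisation stratum (IL-6 antibody use), which can cost power on change-from-baseline endpoints such as IL-6 and CRP but does not bias them

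*Combined protocol and SAP*

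**What the plan says.** Protocol 12.1 states: "Randomization of subjects will be stratified by use of IL-6 antibody therapy". Protocol 15.2 repeats this and places randomisation on the last screening day or the morning of Day 1, so stratum status is known before dosing.

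SAP 10.2 lists five biomarkers as secondary efficacy endpoints: change from baseline in MIF, IL-1β, IL-6, "tumor necrosis factor (TNF- α), and C-reactive protein (CRP) at Day 3, 5, 7 and 14". Change-from-baseline endpoints are analysed by "analysis of covariance (ANCOVA) models with treatment group as a factor and the baseline value of the corresponding endpoint as a covariate". On testing, the section says: "All secondary analyses will be conducted using one-sided tests at the alpha=0.025 level of significance, with no adjustments for multiplicity".

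The stratum enters the analysis in one place only, SAP 10.1: "A supportive analysis for each of the two co-primary endpoints will be conducted using the Mantel-Haenszel test stratified by the randomization stratification variable". SAP 7.6 plans no subgroup analyses. SAP 3.3 describes 1:1 allocation without naming the stratum. SAP 5 sets about 40 participants with no power calculation. The footnotes to SAP 13.1 and 13.2 report 31 and 5 subjects consented.

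**The concern.** A factor is normally chosen for stratification because it is expected to be prognostic. Here it is a therapy directed at IL-6, and IL-6 is itself an endpoint of the anti-inflammatory objective. Of all the endpoints, IL-6 and perhaps CRP are where this factor is most likely to matter.

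Stratified allocation balances the factor between arms. A model without the factor leaves its effect in the residual, so the analysis does not claim the precision that the design provides. The baseline covariate need not repair this, because an antibody may change the course after baseline. With roughly 36 to 40 subjects, a real effect on a marker could be missed. SAP 5 says the results will be used to design later studies, so a missed signal would carry forward.

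**Working it through.** **1. Text.** Stratified by IL-6 antibody use: yes (protocol 12.1, 15.2). Stratum in the supportive test of the co-primaries: yes (SAP 10.1). Stratum in the ANCOVA: no (SAP 10.2).

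**2. Figures in the plan.** No power, effect size or SD is stated for any biomarker, so there is no power figure to reproduce. The equivalence in SAP 7.5 between one-sided 0.025 and two-sided 0.05 is exact (z = 1.960 both ways).

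**3. Assumed inputs.**
- N = 31 + 5 = 36. These are subjects consented; the number sampled may be lower.
- Log scale with residual SD 1. SAP 10.2 names no transformation.
- Drug effect of 0.96 SD, giving about 78% power with the stratum in the model.
- Share of users p, and antibody shift g on the log scale. Neither is in the documents.

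**4. Residual variance without the stratum.** It becomes 1 + p(1−p)g². The sign of g does not matter. For a 5-fold effect, g = ln 5 = 1.609 and g² = 2.590. Under stratified allocation the true sampling variance of the treatment estimate does not grow, but the model standard error is inflated by k, the square root of this quantity. The one-sided size is then about P(Z > 1.960k).

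| Users | 1 + p(1−p)g² | k | Approximate size |
|---|---|---|---|
| 6% (2 of 36) | 1 + 0.0525 × 2.590 = 1.136 | 1.066 | 1.8% |
| 17% (6 of 36) | 1 + 0.139 × 2.590 = 1.360 | 1.166 | 1.1% |
| 33% | 1 + 0.222 × 2.590 = 1.576 | 1.255 | 0.7% |
| 50% | 1 + 0.250 × 2.590 = 1.648 | 1.284 | 0.6% |

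**5. Simulated power**, SAP model against about 78% with the stratum:
- 5-fold effect, 17%, 33% and 50% users: 66%, 60% and 58%, a loss of 12, 18 and 20 points. One-sided size is about 0.6% to 1.2%, in line with the table.
- 5-fold effect, 6% users: a loss of about 4 points.
- 2-fold effect, 17% to 50% users: a loss of about 2 to 4 points.
- 10-fold effect, 17% to 50% users: a loss of about 24 to 38 points. This is an extreme case.
- No users: no loss.

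**6. Cross-check with N = 40 and the shift in residual SDs.** Starting from 80%, a two-sample power formula with the variance of step 4 gives 79% (10% users, 0.5 SD), 73% (25%, 1 SD), 56% (25%, 2 SD) and 51% (50%, 2 SD). Simulation at 25% users and 2 SD gives 55% without the stratum and 79% with it; size is 0.5% and 2.5%.

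**7. Bias from use at randomisation.** In every scenario the mean error of the treatment estimate was within 0.012 SD, which is simulation noise.

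**8. If the list was in fact not stratified.** SAP 3.3 is silent on this. At 25% users and 2 SD, size stays near 2.5% (2.4%), power is 54% without the stratum and 77% with it, and there is still no bias.

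**The case against.** **Few subjects may be users.** Protocol 12.3 excludes immunosuppression with immunosuppressant medications (criterion 2) and recent investigational or off-label medication (criterion 11). How these fit with stratifying on an IL-6 antibody is not explained, and the stratum may be small or empty. This stands, and it is why the loss is given as a range that starts at zero.

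**The antibody effect is not in the documents.** They state no direction or size. The link to IL-6 is plausible from the name of the therapy; the link to CRP is an assumption. This also stands.

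**The endpoints are unadjusted secondary markers in a pilot.** Neither co-primary endpoint nor the success rule is affected, and the error is on the conservative side. This limits the importance of the point but is no reason to omit a factor already used in the allocation.

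**A reader might infer that IL-6 and CRP become biased and partly measure the co-treatment.** For use at randomisation this is wrong (step 7). Bias could arise only if an antibody is started after randomisation at different rates by arm. Protocol 13.8 says only "The use of any unauthorized investigational therapy is prohibited during the study". Whether an IL-6 antibody falls under that depends on its status, which is not given. No rate, arm difference or direction is stated. For scale, 30% of placebo and 20% of ibudilast subjects starting one would move the estimate by 0.10 × g, that is 0.1 SD for g = 1 or 0.2 SD for g = 2. Under a treatment-policy reading that shift is part of the effect, and a baseline stratum term is not meant to remove it. It is a possibility, not something the documents show.

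**Conclusion.** The omission is confirmed by the text. Its consequence is lost power and a conservative test on change-from-baseline endpoints that the antibody shifts, with an unbiased treatment estimate. Under the stated assumptions the loss ranges from none (no users), through at most about 4 points (6% users at a 5-fold effect, or a 2-fold effect), to about 12 to 20 points (17% to 50% users, 5-fold effect). Which of these applies cannot be settled from the documents, because the share of users, the antibody effect and the residual SD are all assumed. The point concerns the precision of secondary biomarkers; it is worth acting on because the remedy costs almost nothing.

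**What to change.** In SAP 10.2, add the randomisation stratum (IL-6 antibody use, yes/no) as a factor in the ANCOVA models, and state that it is dropped if the stratum is empty. Cost: a line of SAP text, one model term and one degree of freedom. In the simulations the adjusted model held its size at about 2.5%.

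Optionally, as a sensitivity analysis for IL-6 and CRP only, use the concomitant-medication dates that SAP 9.2 already lists to flag values drawn after an IL-6 antibody was first given post-baseline. Report the number flagged per arm, and the comparison with and without those values. Excluding them conditions on a post-randomisation event, so the all-values analysis should remain the main one, and no rule should bar interpretation when the two differ. No new data are needed for either step.

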10.3 Exploratory Analysis

Time to discharge

10.4 Pharmacokinetics Analysis

Pharmacokinetic analyses will be performed on plasma samples from eight subjects. Blood samples (approximately 2 mL per sample) will be collected at each time point for the bioanalytical assay of MN-166 and stored frozen at approximately -80°C until shipment is sent to the PK vendor. Blood samples will be assayed for MN-166 using a validated liquid chromatography/tandem mass spectroscopy (LC/MS/MS) method.

10.4.1 Pharmacokinetic Samples

Pharmacokinetic samples will be collected on Day 1: AM Predose, and at 2, 4, 8 and 12 hours (Predose of PM dose), and on Day 3 and Day 5 at AM Predose.

10.4.2 Pharmacokinetic Parameters

The following PK parameters will be calculated using model-independent approaches (NCA) from MN-166 individual plasma concentrations, whenever practical.

Confidential

Parameter	Description of Parameter
t_{max}	Time from the start of dosing at which the maximum concentration was observed
C_{max}	Maximum observed concentration
AUC_{0-t}	Area under the concentration versus time curve from the start of dose administration to the last quantifiable point within the dosing interval
λ_z	Terminal rate constant calculated from the terminal slope of the log-linear regression of concentration with time
$t_{1/2}$	Terminal half-life, calculated as $\ln(2)/\lambda_z$
$AUC_{0-\infty}$	Area under the concentration versus time curve from time 0 to infinity calculated as $AUC_{0-t} + Clast/\lambda_z$, where Clast is the last quantifiable concentration
CL or CL/F	Total body clearance, calculated as Dose/ AUC_{0-t}
V_z or V_z/F	Terminal volume of distribution, calculated as CL/λ_z

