9.3 Treatment Duration Justification

According to CDC, among the COVID-19 patients who developed severe disease, the medium time to dyspnea ranged from 5 to 8 days, the median time to acute respiratory distress syndrome (ARDS) ranged from 8 to 12 days, and the median time to ICU admission ranged from 10 to 12 days. According to the published paper discussing a total of 191 COVID-19 patients treated in Wuhan, China, (Zhou et al 2020 Lancet), the median time from illness to dyspnea was 7.0 days, median time from illness to onset of ARDS was 12 days, and median time from illness to ICU admission was 12 days in total patients. The median time from dyspnea to intubation was 10.0 days (IQR 5.0–12.5) for patients who received invasive mechanical ventilation.

The steady-state plasma ibudilast concentrations are reached within 3 days of initiating b.i.d. and we want to treat at least 5 days with steady state drug level, thus, we determined duration of treatment to be 7 days.

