13.0 TREATMENTS

MN-166 (ibudilast) will be administered as MN-166 50 mg (5 capsules) b.i.d for 7 days. Study drug may be taken with food or within an hour of eating to improve gastrointestinal tolerability. Subjects who cannot tolerate a b.i.d. dosing regimen may be administered a t.i.d. dosing regimen (40 mg at breakfast, 30 mg at lunch, 30 mg dinner). Subjects who cannot tolerate this regimen will be discontinued from the study.

Day 1 study drug may be administered starting with the PM dose. If the first dose of study drug is administered in the PM then the last dose should be administered on Study Day 8 in the AM.

Matching placebo will also be provided and will be administered as 50 mg (5 capsules) b.i.d. for 7 days.

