13.1 Study Drug Supply

MN-166 and matching placebo will be provided in 10 mg non-vegetarian capsules in polyethylene bottles and will be stored at room temperature.

MN-166 is an extended release pharmaceutical preparation comprised of white extended release granules contained in a No.4 white capsule ([Table 3](#)).

Table 3 Study Drug Information

Investigational Drug	MN-166 or matching placebo
Formulation	10 mg capsules
Frequency	MN-166: 50 mg b.i.d. for 7 days
Storage Conditions	Store at room temperature

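### A first-dose profile that ends at 12 h does not reliably support lambda-z, half-life, AUC0-inf or Vz/F, and SAP 10.4.2 gives no rule for when to report them

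*Combined protocol and SAP*

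**What the plan says.** SAP 10.4.2 lists parameters to be obtained by non-compartmental analysis of individual concentrations, as far as practicable. They include lambda-z, defined as "Terminal rate constant calculated from the terminal slope of the log-linear regression of concentration with time", and three quantities built on it: half-life, AUC0-inf and Vz/F. AUC0-t is confined to the dosing interval, CL/F is dose divided by that AUC0-t, and Vz/F is CL/F divided by lambda-z. No minimum number of post-peak points, fit criterion or extrapolation limit is stated.

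Sampling is set in SAP 10.4.1. The serial profile is "Day 1: AM Predose, and at 2, 4, 8 and 12 hours (Predose of PM dose"), so the evening dose ends it. Single samples follow "on Day 3 and Day 5 at AM Predose". No parameter in the 10.4.2 table uses those two troughs. They appear only as concentrations (SAP 2.2.2, SAP 7, protocol 19.5).

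Protocol 13.1 states "MN-166 is an extended release pharmaceutical preparation". Protocol 9.3 states "The steady-state plasma ibudilast concentrations are reached within 3 days of initiating b.i.d". Protocol 8.3 anticipates a steady-state Cmax of about 116 ng/mL and AUC0-24h of about 1613 ng*h/mL at 50 mg b.i.d., from a healthy-volunteer group. No half-life or tmax for MN-166 is given.

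**The concern.** A terminal slope needs several samples taken after absorption and distribution are over. Here the last sample is at 12 h and the product releases drug slowly. If the observed peak is at 2, 4 or 8 h, then 3, 2 or 1 samples follow it. A line can still be fitted to two or three points, and nothing in the SAP stops that value from being tabulated.

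The trial could then report a half-life, AUC0-inf and volume in COVID-19 patients that reflect the sampling window more than the drug. Eight subjects are sampled. The documents do not say that all are on active drug; if sampling is not by arm, 1:1 allocation gives an expected four, and a 36% chance of three or fewer. One aberrant half-life could dominate such a summary. The two troughs could also support a simple accumulation estimate, which bears on the steady-state argument in protocol 9.3, but none is planned.

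**Working it through.** The plan states no half-life, extrapolation share or PK precision, so there is no figure to reproduce.

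**1. What the documents imply about half-life.**
- Protocol 9.3 puts steady state within 72 h. Taking steady state as 5 half-lives, 4 half-lives or 90% of plateau (3.32 half-lives) gives 72/5 = 14.4 h, 72/4 = 18.0 h and 72/3.32 = 21.7 h. Because the statement says within, these are upper bounds.
- Protocol 8.3: Cavg = 1613/24 = 67.2 ng/mL, and Cmax/Cavg = 116/67.2 = 1.73. In a one-compartment model with instantaneous input, Cmax/Cavg = 12k/(1 - exp(-12k)). Setting this to 1.73 gives k = 0.101/h, a half-life of 6.9 h. Slower input flattens the peak and needs a shorter half-life still. So these figures point to about 7 h or less, or to more than one compartment.

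**2. Share of AUC0-inf beyond 12 h.** With one compartment and first-order input (rate ka), the share is [ka exp(-12k) - k exp(-12ka)]/(ka - k). The ka and tmax values are assumed.
- Half-life 6 h (k = 0.1155): 27% at tmax 2 h. At ka = 0.2/h it is (0.2 x 0.250 - 0.1155 x 0.0907)/0.0845 = 47%.
- Half-life 14.4 h: 58% at tmax 2 h.
- Half-life 18 h (k = 0.0385), ka = 0.2/h: (0.2 x 0.630 - 0.0385 x 0.0907)/0.1615 = 76%.
- With instantaneous input the share is 2^(-12/half-life). It reaches 20% at 12/log2(5) = 5.2 h. Absorption delay only raises it, so in this model a share below 20% needs a half-life of about 5 h or less with fast input.

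**3. Half-life from the 4, 8 and 12 h points.** With equal spacing the regression gives 8 ln2/ln(C4/C12). The table shows the noise-free value, then the 5th-95th percentiles from 4,000 simulated profiles with 15% CV per concentration (slope results among profiles with a positive lambda-z). The last column is the half-life from the ratio of the Day 5 trough to the Day 1 12 h sample.

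| True half-life, tmax (assumed) | AUC0-inf after 12 h | Slope, noise-free | Slope, 5th-95th | Accumulation, 5th-95th |
|---|---|---|---|---|
| 6 h, 2 h | 27% | 6.0 h | 4.4-9.6 h | 2.8-11.3 h |
| 6 h, 4 h | 33% | 8.5 h | 5.6-17.9 h | 2.8-11.4 h |
| 6 h, 6 h | 44% | 25.5 h | 9.3-160.5 h | 3.1-12.5 h |
| 14.4 h, 2 h | 58% | 14.4 h | 7.5-61.2 h | 8.3-24.3 h |
| 14.4 h, 4 h | 60% | 17.5 h | 8.4-94.0 h | 8.5-23.6 h |
| 14.4 h, 6 h | 64% | 45.8 h | 11.0-258.3 h | 8.6-24.2 h |

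At 14.4 h, 3-28% of profiles give no positive lambda-z. At 6 h the accumulation half-life is undefined (R at or below 1) in 5-9%.

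**4. Error in the other direction.** Two-compartment settings that fit both the protocol 8.3 exposures and a 10-18 h terminal half-life give a 12 h slope half-life of 3.0-6.3 h, against 4.8-16.9 h by accumulation. One example uses a distribution half-life of 1.5 h, a terminal half-life of 14.4 h, half of the AUC in each phase and ka = 0.6/h. It gives Cmax/Cavg = 1.73. In units of dose/(CL/F) per hour, C4 = 0.0863 and C12 = 0.0178, so the slope half-life is 5.545/ln(0.0863/0.0178) = 3.5 h.

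**5. Vz/F.** Dose/AUC0-12 overstates CL/F by 1/(1 - share). At 6 h this is 1/(1 - 0.274) = 1.38 to 1/(1 - 0.438) = 1.78; at 14.4 h it is 1/(1 - 0.576) = 2.36 to 1/(1 - 0.637) = 2.75. Vz/F carries this error and that of lambda-z.

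**6. The accumulation formula.** If absorption is nearly complete at 12 h, R = C(predose Day 5)/C(12 h Day 1) and effective half-life = 12 ln2/ln(R/(R - 1)). At a true 14.4 h, R = 2.26 after eight doses, giving 8.318/ln(2.26/1.26) = 14.2 h.

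**The case against.** The strongest reply is that the kinetics are unknown and may be favourable. A reader might infer from the 3-day statement that half-life is 14-18 h and that the whole profile is shorter than one half-life. The documents do not support that: the statement is only an upper bound, and the protocol 8.3 exposures point lower in a one-compartment model. At half-lives of 3-5 h with fast input, the slope is within 30% of truth in about 62-96% of simulated subjects, and the accumulation method in only 21-41%. This stands. It rules out saying that the parameters cannot be derived at all, or that half-life is always overstated.

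It does not rescue the plan. The same exposures also fit two-compartment kinetics, where the slope is too steep, and nothing in the SAP would tell the reader which case applies.

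Second, the SAP calculates parameters only where practicable, so an analyst may leave some out. That is true, but without criteria the choice is made after seeing the data.

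Third, a reader might infer that the Day 3 and Day 5 troughs are ignored. They are not: SAP 7 summarises data at each time-point, so both will be reported. What is missing is a derived parameter and a stated comparison.

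Finally, this is descriptive PK in eight subjects of a pilot. That limits the importance, not the validity.

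**Conclusion.** The concern holds in this form: lambda-z, half-life, AUC0-inf and Vz/F cannot be reliably estimated from the planned profile, and the SAP has no acceptance criteria to separate usable values from artefacts. The direction of error in half-life depends on the true kinetics. More than 20% of AUC0-inf is extrapolated in most settings examined. The exceptions are half-lives of about 5 h or less with fast input and some fast-distribution two-compartment settings. Vz/F is affected in two ways, through lambda-z and through the truncated clearance.

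The sizes rest on assumed half-lives, input rates and 15% concentration error, because the documents give none of these. The structural facts come from the documents: a 12 h first-dose profile, an extended-release product, no acceptance criteria, and troughs that enter no listed parameter. This is a worthwhile improvement to a descriptive analysis. It does not threaten the trial's efficacy conclusions.

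**What to change.** Amend SAP 10.4.2 as follows.

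- Make Day 1 Cmax, tmax and AUC0-12 the primary PK parameters.
- Drop Vz/F as defined.
- Report lambda-z, half-life and AUC0-inf only for subjects meeting pre-specified criteria, for example at least three points after the peak, an adequate fit and no more than 20% extrapolation. Label them as apparent 12 h values and state how many subjects qualify.
- Add R = C(predose Day 5)/C(12 h Day 1), and effective half-life = 12 ln2/ln(R/(R - 1)) where R > 1. Restrict both to subjects with a morning first dose and an unchanged b.i.d. regimen to the Day 5 sample, since protocol Table 1 allows an evening start and protocol 13.0 allows a t.i.d. regimen. Report how many have R at or below 1.
- State that the Day 3 and Day 5 troughs will be compared as the steady-state check.

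The cost is SAP wording, with no new samples. Few or no subjects may qualify for terminal parameters: three points after the peak requires an observed peak at 2 h. The effective half-life assumes linear kinetics and near-complete absorption by 12 h. It is imprecise or undefined when half-life is about 6 h or less, and it does not replace lambda-z, AUC0-inf or Vz/F.

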19.5 Pharmacokinetic Analysis

Plasma concentrations of MN-166 will be summarized.

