2.2.2 Secondary Outcome Variable(s)

- Proportion of subjects free from respiratory failure as defined by free from supplemental oxygen requirement (invasive mechanical ventilation, non-invasive ventilation, high-flow oxygen, or ECMO, CPAP, BiPAP, nasal cannula) at Days 14, 28 and Day 60*
- Proportion of subjects with mechanical ventilation /intubation at Days 7, 14, 28 and Day 60*
- Changes from baseline in clinical status using the NIAID 8-point ordinal scale and discharged record at Days 7, 14, 28 and 60*
- Proportion of subjects with at least a one-point improvement in clinical status using the NIAID 8-point ordinal scale and discharge record at Days 14, 28 and 60*
- All-cause mortality at Days 28 and Day 60*
- Proportion of the subjects discharged from hospital at Days 7, 14, 28 and 60*
- Change from baseline in migration inhibitory factor (MIF), (interleukin 1-beta (IL-1 β), interleukin 6 (IL-6), tumor necrosis factor (TNF- α), and C-reactive protein (CRP) at Day 3,5,7 and 14
- Incidence, frequency, and severity of adverse events at Day 7, 14, 28 and Day 60*
- Change from baseline of the following parameters at Days 7, 14 and Day 60*:
 - o ALT
 - o AST

Confidential

- o Serum creatinine
- o BUN
- o Complete blood count
- o Total bilirubin
- o D-dimer
- PK plasma concentrations and parameter (PK population)

*Intubated subjects only on Study Day 60

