6 ANALYSIS POPULATIONS

The following analysis populations are planned for the studies:

- **Full Analysis Set (FAS)** will include all randomized subjects.
- **Safety Analysis Set (SAS)** will include all randomized subjects who received at least one dose of study drug and had at least one post-dose safety assessment.
- **Per Protocol Analysis (PP):** will consist of the FAS subjects excluding those with major protocol violations.

Confidential

- **Pharmacokinetic Population (PK):** will consist of the subjects for which PK collection was performed. Eight subjects are anticipated to participate in PK sample collection.

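### SAP 10.4.2 divides dose by a first-dose AUC that stops within 12 hours, so the reported CL/F and Vz/F exceed the values based on AUC0-inf, which the same table defines but does not use

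*Combined protocol and SAP*

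**What the plan says.** SAP 10.4.2 lists the parameters to be derived by non-compartmental analysis. Three rows matter:

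- AUC0-t: "Area under the concentration versus time curve from the start of dose administration to the last quantifiable point within the dosing interval".
- AUC0-inf: "Area under the concentration versus time curve from time 0 to infinity calculated as" AUC0-t + Clast/lambda_z.
- CL/F: "Total body clearance, calculated as Dose/ AUC_{0-t"}. The next row sets Vz/F to that clearance divided by lambda_z.

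SAP 10.4.1 gives the sampling: "Pharmacokinetic samples will be collected on Day 1: AM Predose, and at 2, 4, 8 and 12 hours (Predose of PM dose"), then one predose sample on Day 3 and one on Day 5. Protocol 14.4 has the same schedule. Footnote c of the schedule of assessments (protocol Table 1) puts the Day 1 predose sample before morning dosing, so the serial profile follows the first dose.

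SAP 2.2.2 lists "PK plasma concentrations and parameter (PK population") among the secondary outcomes. Protocol 19.5 promises less: "Plasma concentrations of MN-166 will be summarized". SAP Section 1 makes the SAP authoritative on data analysis.

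**The concern.** Dose divided by the AUC over one dosing interval equals CL/F only at steady state, when that AUC equals the single-dose AUC0-inf. After a first dose, the drug still in the body at the last sample is missing from AUC0-t. The denominator is then too small and the clearance too large. The SAP computes the missing piece, Clast/lambda_z, for AUC0-inf, but does not carry it into CL/F.

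The shift has the same direction in every subject for whom the parameter is calculated, so averaging does not remove it. SAP Section 5 says the results will be used to design later studies. A clearance raised by its own definition could also be misread as a difference from the healthy-volunteer exposure quoted in protocol 8.3.

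**Working it through.** **No plan figure to reproduce.** The documents state no CL/F, half-life or extrapolated share.

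**Step 1: is there a steady-state interval?** Serial samples exist only at 0, 2, 4, 8 and 12 h on Day 1. Protocol 9.3 says steady state is reached within 3 days of twice-daily dosing. Days 3 and 5 have one sample each, from which no interval AUC can be formed. So the formula can only be applied to the first-dose profile.

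**Step 2: exact ratio of the two estimates.** Let s = (Clast/lambda_z)/AUC0-inf, the estimated extrapolated share. Then AUC0-t = (1 - s) × AUC0-inf, and

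(Dose/AUC0-t) / (Dose/AUC0-inf) = 1/(1 - s).

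This is 1.11 at s = 0.10, 1.25 at 0.20 and 2.00 at 0.50. It exceeds 1 whenever Clast is quantifiable and lambda_z is positive. Because Vz/F = CL/lambda_z, its factor is the same.

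**Step 3: scale from protocol 8.3** (approximate healthy-volunteer steady-state values at 50 mg b.i.d.):

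- CL/F = 100 mg / 1613 ng·h/mL = 62.0 L/h.
- Cavg = 1613/24 = 67.2 ng/mL, so Cmax/Cavg = 116/67.2 = 1.73.
- A clearance of 62.0 L/h would be reported as 62.0/0.80 = 77.5 L/h at s = 0.20, and as 62.0/0.50 = 124 L/h at s = 0.50.

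**Step 4: range for the share beyond 12 h (assumption).** One compartment, first-order absorption at rate ka, 12 h interval.

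(a) Half-life solved so that steady-state Cmax/Cavg = 1.73. The last two columns apply linear trapezoids to the planned samples, with the slope fitted to 4, 8 and 12 h.

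| ka (/h) | half-life (h) | true share beyond 12 h | 1/(1 - true share) | SAP CL/F ÷ true | Dose/AUC0-inf ÷ true |
|---|---|---|---|---|---|
| 0.4 | 2.07 | 6.8% | 1.07 | 1.11 | 1.01 |
| 1.0 | 3.83 | 13.9% | 1.16 | 1.23 | 1.04 |
| 2.0 | 4.89 | 19.7% | 1.24 | 1.36 | 1.07 |
| 5.0 | 5.83 | 24.6% | 1.33 | 1.50 | 1.10 |

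On the planned samples the estimated shares are 9%, 15%, 21% and 27%. The ratio of the SAP value to Dose/AUC0-inf is then 1.10, 1.18, 1.27 and 1.37, as Step 2 requires.

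(b) Longer half-lives, assumed freely. Four to five half-lives in 72 h would be 18 to 14.4 h, but 3 days is only an upper bound on the time to steady state. Entries are 1/(1 - true share):

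| half-life (h) | bolus | ka 0.5/h |
|---|---|---|
| 6 | 1.33 | 1.48 |
| 12 | 2.00 | 2.30 |
| 18 | 2.70 | 3.15 |

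Still slower absorption gives more: 3.56 at ka 0.3/h and 18 h. The models in (b) with absorption have a flatter steady-state profile than the 1.73 from protocol 8.3, about 1.1 to 1.3.

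**Step 5: does AUC0-inf recover the true value?** Not always. In (a) it is 1 to 10% too high. With ka 0.5/h it gives 0.92, 0.74 and 0.55 of true CL/F at half-lives of 6, 12 and 18 h, because continuing absorption flattens the 4 to 12 h slope. With ka 0.3/h and 12 h it gives 0.14 of true, against 2.66 for the SAP formula. With ka 0.3/h and 14.4 h the fitted slope has the wrong sign and lambda_z is not estimable.

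**The case against.** The strongest reply is that little depends on this. Pharmacokinetics is descriptive and covers eight sampled subjects. The SAP's lists of tables and listings (13.3 and 13.4) contain no pharmacokinetic output, so no listed display would carry CL/F. The parameters are derived from "MN-166 individual plasma concentrations, whenever practical". All of this stands and caps the point at minor. It does not repair the definition: the practicality clause governs whether a parameter is calculated, not which formula is used.

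A second reply is that AUC0-inf is not a safe denominator here. This also stands. Protocol 13.1 describes an extended-release product, and at most three samples inform the slope. Step 5 shows error in both directions, and one case where the SAP formula lies closer to the truth. The remedy therefore needs an estimability condition as well as a new denominator.

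A reader might infer that 1/(1 - share) is the overstatement of true clearance. It is not: it is the ratio of two estimates from the same samples. At ka 5/h the true share gives 1.33, while the SAP formula on the planned samples gives 1.50 times true CL/F.

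A reader might also infer a gap over placebo subjects, since the PK population "will consist of the subjects for which PK collection was performed", or over subjects whose dosing starts in the evening. Neither adds to this point. The parameters come from measured MN-166 concentrations, which placebo subjects do not supply, and the sampling footnote presupposes a morning start.

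**Conclusion.** Wrong as written; minor. The CL/F and Vz/F definitions do not fit the only profile the trial collects, and no other section limits or corrects them. The excess over Dose/AUC0-inf, 1/(1 - estimated extrapolated share), is exact algebra and needs no model.

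Its numerical size is not established. The range from about 1.07 (models matched to the healthy-volunteer Cmax/Cavg) to about 3 (half-lives up to 18 h with slower absorption) rests on assumed one-compartment kinetics and on half-lives the documents do not give. No single figure within it should be quoted as the error.

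Cmax, tmax, AUC0-t and the Day 3 and Day 5 troughs are unaffected. The documents do not support any inference that an efficacy or safety conclusion is at risk.

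**What to change.** In SAP 10.4.2:

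1. Define CL/F as Dose/AUC0-inf, and Vz/F as that CL/F divided by lambda_z.
2. Report the extrapolated share of AUC0-inf beside each value.
3. State that lambda_z, t1/2, AUC0-inf, CL/F and Vz/F are reported only where the 4 to 12 h data support a terminal slope. Otherwise report Cmax, tmax, AUC0-12 and the Day 3 and Day 5 troughs.
4. Note that the corrected CL/F can be too high if a slower phase is missed, or too low if absorption continues into the slope window.

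Any numeric limit on the extrapolated share is the sponsor's choice and would not guarantee accuracy.

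Cost: corrected definitions in the parameter table, one added column and a short statement on estimability. No extra samples are needed, since Vz/F already requires lambda_z. The downside is that some parameters may not be estimable for some subjects.
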